13.3.3 Centre analyses

This investigation is a multi-centre investigation. However, there is no a priori reason to suspect that there will be any qualitative differences between the study sites regarding any of the outcome variables in the study. Therefore, primary statistical analysis will not include centre in the model but analyses may be stratified by centre as applicable.

13.3.4 Analysis sets

All treated patients will be included in the Safety Analysis Set (SAS).

All correctly, included patients will be included in the Intention-To-Treat (ITT) analysis set.

Patients who have been treated according to the protocol without any major deviations will be included in the Per Protocol (PP) analysis set.

The primary efficacy analysis set will be PP. However, it is expected the SAS, ITT and PP analysis sets will be identical in this study.

The primary efficacy objective of the investigation will be analysed using data from patients in the PP analysis set as well as using data from patients in the ITT analysis set. The conclusion will be based on data from the primary efficacy analysis set and the analysis based on data from the other efficacy analysis set will be considered as a sensitivity analysis.

The secondary efficacy objectives will be analysed using data from the primary efficacy analysis set only.

The analyses of the safety objectives will be based on data from the SAS.

13.3.5 Statistical analyses during the course of the study

No analyses will be conducted during the course of the study.

13.4 Pass/fail criteria

The hypothesis is that aScope™ 4 Broncho will be preferred compared to the standard reusable or single-use bronchoscopes available at the involved sites.

This study is considered passed if a minimum of 60% of the device evaluations show that aScope™ 4 Broncho is preferred for the clinical procedure or at least on par based on the investigators memory of their use of standard bronchoscopes.

For the secondary end-points, at least 80% of the evaluations must be at the level of acceptable, good/very good or easy/very easy or slightly better/much better/no difference.

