2. AIM

The aim of this study is to obtain a broad user perspective of the aScope™ 4 Broncho, focusing on the device functionalities within regular clinical practice and therapeutic use of flexible bronchoscopes in the OR and ICU.

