3. HYPOTHESIS

The hypothesis is that aScope™ 4 Broncho will be preferred compared to the standard methods (i.e. reusable or single-use bronchoscopes) available at the involved sites.

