4. END POINT

All endpoints are qualitative assessments based on the actual use of aScope™ 4 Broncho during this study, or the investigators memory of use of their standard bronchoscopes.

Primary end-point:

- Preference, based on the investigators memory of their standard bronchoscope
 - The investigator will be asked: "In your memory, compare your daily bronchoscope and the aScope 4 Broncho just evaluated;
Which bronchoscope would you **prefer** for this procedure?"

Secondary end-points:

- Ease of Navigation and Advancement within the bronchial tree with or without endoscopic tools (on a 5 grade scale: *Very Difficult*, *Difficult*, *Acceptable*, *Easy*, *Very Easy* and compared to memory *Much better*, *Slightly better*, *No difference*, *Slightly worse*, *Much worse*)

- Ease of Manoeuvrability within the upper airway (on a 5 grade scale: *Very Difficult, Difficult, Acceptable, Easy, Very Easy* and compared to memory *Much better, Slightly better, No difference, Slightly worse, Much worse*)
- Manoeuvrability with tools in the working channel (on a 5 grade scale: *Very Poor, Poor, Acceptable, Good, Very Good*)
- Perception of Image quality channel (on a 5 grade scale: *Very Poor, Poor, Acceptable, Good, Very Good* and compared to memory *Much better, Slightly better, No difference, Slightly worse, Much worse*)
- Perception of Ergonomics (on a 5 grade scale: *Very Poor, Poor, Acceptable, Good, Very Good* and compared to memory *Much better, Slightly better, No difference, Slightly worse, Much worse*)
- Perception of Suction capability (on a 5 grade scale: *Very Poor, Poor, Acceptable, Good, Very Good* and compared to memory *Much better, Slightly better, No difference, Slightly worse, Much worse*)
- Overall perception of functionality (on a 5 grade scale: *Very Poor, Poor, Acceptable, Good, Very Good*)
- Potential to replace exiting standard bronchoscope (Yes, No)
- Adverse events and device deficiencies

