7. PROCEDURE

During normal clinical procedures within the OR or ICU where a bronchoscopy is requested, the investigator shall decide which bronchoscope (type/model) should be used for the patient/procedure as soon as possible. If the aScope™ 4 Broncho is chosen the provided evaluation form should be completed after finalising the clinical procedure. As the study follows everyday clinical procedures at the selected sites, the patients will adult patients admitted to the OR or ICU, undergoing at least one bronchoscopy procedure.

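### Does pooling preference over reusable and single-use daily bronchoscopes, with no breakdown by type, undermine the 60% pass rule?

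*Combined protocol and SAP*

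**What the plan says.** Section 3 (Hypothesis) sets aScope 4 against the "standard methods (i.e. reusable or single-use bronchoscopes) available at the involved sites". Section 13.4 repeats this beside the pass rule: aScope 4 is expected to be "preferred compared to the standard reusable or single-use bronchoscopes available at the involved sites". The primary question in section 4 reads "In your memory, compare your daily bronchoscope and the aScope 4 Broncho just evaluated" and then asks which scope the rater would prefer for this procedure. Five secondary endpoints also carry a compared-to-memory scale: navigation, upper-airway manoeuvrability, image quality, ergonomics and suction.

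Section 13.4 applies one 60% rule to all device evaluations (preferred or at least on par). For the secondary endpoints, "at least 80% of the evaluations must be at the level of acceptable" or one of the other listed favourable grades, which include the compared-to-memory answers from no difference upwards.

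Section 13.3.1 plans descriptive statistics as applicable. On strata, section 13.3.3 says only that the "primary statistical analysis will not include centre in the model but analyses may be stratified by centre as applicable". Section 13.1 states that no sample size calculation was done. No section specifies a breakdown by comparator type, and none rules one out. The evaluation form is not reproduced, so whether it records the type cannot be seen.

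**The concern.** There is no concurrent control (section 5.4), so the remembered scope is the only reference behind every comparative answer. The plan itself names two kinds of reference and then merges them. Raters used to a reusable scope and raters used to another single-use scope may well answer differently.

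If so, the pooled share depends on how many forms come from each group. A pass could rest on a strong result against one type and a weak one against the other, and a reader might take it to hold against both. Optional stratification by centre separates the types only where a site uses a single, known type.

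**Working it through.** **Inputs.** From the documents: 175 evaluable forms (section 5.2, as amended) and thresholds of 60% and 80% (section 13.4). The documents state no power or precision figure, so there is none to reproduce. Assumed here: the comparator mix, the favourable rate against each type, and independent forms. Favourable means preferred or at least on par.

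**1. Pass marks.** 0.60 × 175 = 105 and 0.80 × 175 = 140.

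**2. What a pass can conceal.**
- 60% rule: 51/60 = 85.0% (exact 95% CI 73.4 to 92.9%) leaves 105 − 51 = 54 favourable among 175 − 60 = 115, or 47.0% (37.6 to 56.5%). The second interval includes 50%, so this is a low observed rate, not a demonstrated majority against aScope 4.
- More extreme: 98/140 (70%) with 7/35 (20%) also gives 105/175.
- 80% rule: 57/60 (95.0%) leaves 140 − 57 = 83 among 115, or 72.2%.

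These splits are constructed to show what is possible. They say nothing about what is likely.

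**3. How far the mix moves the chance of passing.** Let n₁ forms concern the first type. The chance is P(X₁ + X₂ ≥ 105), with X₁ ~ Bin(n₁, p₁) and X₂ ~ Bin(175 − n₁, p₂), by exact convolution. The true pooled rate is [n₁p₁ + (175 − n₁)p₂]/175. The two mixes are 52 forms (about 30%) and 88 forms (about 50%).

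| Assumed p₁ / p₂ | Pooled rate, n₁ = 52 | Chance of passing | Pooled rate, n₁ = 88 | Chance of passing |
|---|---|---|---|---|
| 75% / 50% | 57.4% | 0.27 | 62.6% | 0.79 |
| 65% / 55% | 58.0% | 0.32 | 60.0% | 0.54 |
| 60% / 60% | 60.0% | 0.53 | 60.0% | 0.53 |
| 75% / 65% | 68.0% | 0.99 | 70.0% | 1.00 |

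First row: (52 × 0.75 + 123 × 0.50)/175 = 100.5/175 = 57.4%, and (88 × 0.75 + 87 × 0.50)/175 = 109.5/175 = 62.6%. The chance of passing follows the pooled rate across the 60% line. Where the two rates are equal, or both clearly above 60%, the mix has little or no effect.

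**4. What a table by type would deliver.** At a common 60% rate, the exact 95% half-width is 17.0 points at 21/35, about 13 at 36/60 and 9.3 at 69/115, against 7.5 at 105/175. It would probably be wider if raters return several forms.

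**The case for a change.** The strongest case for a change is that the documents themselves single out the two types, so this is not an arbitrary subgroup. Recording the type costs one field per form, and reporting it costs two table columns. The type may be hard to recover after the forms are completed. Centre stratification is optional, and section 13.3.3 justifies leaving centre out without considering that the comparator may differ between sites. Reporting what the remembered scope was would also fit the aim in section 2 to "obtain a broad user perspective of the aScope".

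Much of this stands. A pooled pass does not show the result against each type, and centre is only a partial proxy. But it is an argument for an informative extra table, not evidence that the planned analysis misleads on its own question. That data capture is missing cannot be asserted, because the form is not visible. If the type is recorded, the analyst can add the table at reporting in this purely descriptive study without affecting any error rate.

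Section 7 might seem to show that a rater has several usual scopes, since "the investigator shall decide which bronchoscope (type/model) should be used for the patient/procedure". It concerns the scope used in the current procedure, whereas the primary question refers to a single daily scope, so it adds no support.

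**Conclusion.** The concern describes the text correctly, but no change to the plan follows. The target is preference over whatever standard the rater normally uses, and the pooled 60% and 80% rules measure that over the observed mix. The movement from 0.27 to 0.79 in the chance of passing is the rule responding to a true pooled rate on either side of its threshold. It requires an assumed 25-point gap between types straddling 60%; two of the four assumed scenarios show essentially no effect.

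No claim against reusable or single-use scopes alone is planned, and a breakdown without its own criterion could not change pass or fail. What remains is a limit on reading: a pass describes the comparator mix met in the study and should not be quoted against either type separately.

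This rests on the hypothesis meaning site standards taken together, as sections 3 and 13.4 word it. The figures also assume independent forms and mixes and rates that the documents do not give. If a claim against one type were later made, the pooled figure would not support it.

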5.2 Sample size

The study will include a minimum of 100 (amended to 175) adult patients admitted to the OR or ICU undergoing at least one bronchoscopy procedure.

The inclusion will stop when 100 (amended to 175) fully evaluable patients or a maximum of 150 (amended to 200) patients have been enrolled.

The aim is for each site to enroll a minimum of 10 patients.

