11. EVALUATION FORM

The evaluation form is in English and should be filled in English when possible. Missing data not recorded on the day of the procedure should be filled in no later than one week after the procedure, accompanied by date and signature. Data that are evaluated as incorrect by Investigator should be crossed over with ink allowing the "old data" to be seen (example). The Investigator shall then write the new and correct data and then sign and date.

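### The hypothesis is that aScope 4 will be preferred, but the 60% pass rule also counts ties; if the evaluation form allows a tie, a pass does not by itself show preference

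*Combined protocol and SAP*

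**What the plan says.** - **Hypothesis.** Section 3: "The hypothesis is that aScope™ 4 Broncho will be preferred compared to the standard methods". Section 13.4 repeats it just before the pass rule: "The hypothesis is that aScope™ 4 Broncho will be preferred compared to the standard reusable or single-use bronchoscopes". Neither sentence mentions parity.
- **Primary endpoint.** Section 4 makes preference the only primary endpoint. The question begins "In your memory, compare your daily bronchoscope and the aScope 4 Broncho just evaluated" and then asks which scope the investigator would prefer for the procedure. Section 4 gives response options for the secondary ratings but none for this question.
- **Pass rule.** Section 13.4 passes the study if "a minimum of 60% of the device evaluations show that aScope™ 4 Broncho is preferred for the clinical procedure or at least on par", judged against the investigator's memory of standard scopes.
- **Secondary rule.** The 80% rule in section 13.4 also credits ties: "slightly better/much better/no difference".
- **Reporting.** Section 13.3.1 plans frequencies and percentages for categorical primary and secondary endpoints. Section 13.3.4 says "The conclusion will be based on data from the primary efficacy analysis set".
- **Form.** Section 11 describes how the form is completed ("The evaluation form is in English and should be filled in English when possible"), but its items are not reproduced.
- **Size.** Section 5.2: "The inclusion will stop when 100 (amended to 175) fully evaluable patients or a maximum of 150 (amended to 200) patients have been enrolled".

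**The concern.** The hypothesis and the success rule stand in adjacent sentences of section 13.4 and describe different claims. The hypothesis is that users favour aScope 4. The rule is met when enough users do not favour the standard scope. No section sets a minimum share for preference alone, compares the two preference counts, or says what a pass supports.

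If a tie can be recorded, the plan followed exactly could declare the study passed, under a hypothesis of preference, when investigators named the standard scope more often than aScope 4. The primary outcome is one subjective answer from memory without a concurrent control, so what a pass allows the sponsor to say is the main product of the study.

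**Working it through.** **Inputs.** The threshold is 60% (section 13.4). The number of evaluations n is 175, with 200 as the upper limit (section 5.2). The documents give no derivation of the 60%, no sample size calculation (section 13.1) and no expected share of ties, so there is no planned figure to reproduce. Write A, T and S for the counts preferring aScope 4, on par, and preferring the standard scope.

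**Step 1: the rule in counts.** A pass needs A + T ≥ r, with r = 0.6 × n.
- n = 175: r = 105, so S may be as high as 175 − 105 = 70.
- n = 200: r = 120, so S may be as high as 80.

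The rule limits only S. With ties allowed, A = 0, T = 105, S = 70 is a pass.

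**Step 2: ties needed for a pass with the standard scope named more often.** This needs S ≤ n − r and A ≤ S − 1. Then S + A ≤ 2(n − r) − 1, so T ≥ n − 2(n − r) + 1 = 2r − n + 1.
- n = 175: 2 × 105 − 175 + 1 = 36 ties (36/175 = 20.6%), for example 69 aScope 4, 36 on par, 70 standard.
- n = 200: 2 × 120 − 200 + 1 = 41 ties (41/200 = 20.5%), for example 79, 41, 80.

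**Step 3: a two-way form.** With T = 0 a pass needs A ≥ 105 of 175, which leaves S ≤ 70. A pass then does show at least 60% preference, and the reversal in step 2 cannot occur.

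**Step 4: how often, under assumed tie shares.** Take a device with no net preference, expected tie share t, and (1 − t)/2 preferring each scope. Treat evaluations as independent. The chance that one answer counts toward the 60% is t + (1 − t)/2 = 0.5 + t/2. P(pass) is the binomial probability of at least 105 of 175. The last column sums the trinomial over outcomes with a pass and S > A.

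| Expected tie share t | 0.5 + t/2 | P(pass) | P(pass and standard named more often) |
|---|---|---|---|
| 0% | 0.50 | 0.5% | 0% |
| 10% | 0.55 | 10.5% | 0.0% |
| 20% | 0.60 | 53.3% | 7.4% |
| 30% | 0.65 | 92.8% | 41.0% |
| 33.3% | 0.667 | 97.3% | 45.5% |

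At n = 200 the last column is 0, 0.0, 7.4, 42.2 and 46.3%.

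Step 2 concerns the observed number of ties and step 4 the expected share. An expected 20% of 175 is 35 ties, one short of 36. Chance variation can carry the observed count past 36, which is why the 20% row shows 7.4% and not zero.

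**Step 5: a less-preferred device.** For an assumed true split of 25% aScope 4, 40% on par and 35% standard, the chance that one answer counts is 0.65, so P(pass) is again 92.8% at n = 175.

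**The case against.** The strongest reply is that the harm depends on a form not in the documents. The primary question reads most naturally as naming one of two scopes. If the form offers only those answers, the rule demands at least 60% actual preference and the reversal is impossible. This stands, and the conclusion has to be conditional on it. A defect remains even then: section 13.4 refers to parity, the primary item cannot supply it, and section 4 does not say where it would come from.

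Second, the rule is pre-specified and printed beside the hypothesis, and the secondary rule credits ties too. Counting ties is therefore a consistent and open choice. This also stands, and it is why the threshold need not change. But pre-specifying the rule does not make preferred-or-on-par evidence of preferred.

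Third, section 13.3.1 already plans percentages for the primary endpoint, so the three-way split would probably be reported if ties are recorded. That is largely right. What is missing is a link between that split, the pass statement and the use of the word preferred.

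A reader might infer that the sponsor plans to report any pass as proof of preference. The documents do not support that. Section 13.4 says only that the study is considered passed, and the sentence about the conclusion in section 13.3.4 selects the analysis set. Nor is this an inflated type I error: the study is descriptive and states no test or significance level.

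**Conclusion.** The mismatch in wording is certain from the text; its consequence is conditional. If the form allows a tie, a pass shows that at least 60% of evaluations were preferred or on par. It can occur with no stated preference for aScope 4 (0/105/70), or with the standard scope named more often once at least 36 of 175 or 41 of 200 observed answers are ties. These counts are exact and need no model. The probabilities rest on assumed tie shares, an assumed split of preferences and independent evaluations. They show that the problem is negligible at an expected 10% of ties and frequent at about 30%.

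The tempting stronger reading, that a pass can never mean preference, is not supported, because under a two-way form it would mean exactly that.

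The point should be fixed if the form allows ties. If it does not, this is a minor correction of wording.

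**What to change.** Keep the 60% threshold.

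1. In section 4, state which answer to the primary question counts as on par. If the form has no such answer, delete the on-par words from section 13.4; the hypothesis can then stay as it is.
2. If ties are allowed, reword the hypothesis and the pass conclusion in sections 3 and 13.4 to preferred or at least on par, and add that a pass alone does not show preference.
3. Report the percentages preferring aScope 4, on par and preferring the standard scope beside the pass result. Call aScope 4 preferred only when it is named more often than the standard scope, worded as an observed count.

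The cost is wording in three sections and one table, with no extra patients or data. The downside is that a pass supports a weaker claim. The label in item 3 is not proof either: under the step 4 model a neutral device would pass and be named more often in about 44% of studies at an expected 20% of ties, and in about 48% at one third. It must therefore not be presented as a test result.

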13.5 Data file

The Sponsor will file the original evaluation forms for rest of the products' lifetime + 5 years. Moreover, study related documents, e.g. protocol, statistical analysis, report will also be filed.

